Adolescents will be evaluated for treatment non-response to the BEI at 6, 9, 12, 15, and 18 months posttreatment. Non-response is defined as non-normative use of alcohol, marijuana, or other drugs in the past 90 days. Alcohol and marijuana are the outcomes of interest in this study; however, non-normative use of any psychoactive substance will be considered non-response. Alcohol use norms by age are presented in Table 4 and any marijuana use in adolescence is considered non-normative (NHSDAH, 2007). Tobacco and caffeine products are excluded from consideration. For alcohol, marijuana, and other drugs, frequency and quantity of substance use will be collected for the past 90-days using the Substance Use Questionnaire (SUQ). Adolescents who do not demonstrate a response to the BEI at the 6, 9, 12, 15, or 18 month assessment (i.e., use substances at non-normative levels) will be randomized to either (1) No Additional Treatment Monitoring Group, (2) Parent Training/Adolescent CBT (PT/ACBT; e.g., 12 weeks of parent training and adolescent CBT) (3) PT/ACBT plus concurrent stimulant medication (PT/ACBT+MED). Adolescents who demonstrate immediate initial response will be released from treatment and assigned to a monitoring condition in which they are reassessed at 9, 12, 15, and 18 months. Any adolescent who demonstrates non-normative use at any of the follow-up assessments as defined above will be immediately eligible for randomization to further treatment (as detailed above). Adolescents and parents will complete an assessment battery at the randomization point as outlined in Table 5 unless randomization occurs immediately following the 6 or 12 month assessment (in which case the measures will not need to be repeated).

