Follow-up Assessment and Interventions. The schedule of assessment and interventions will depend upon participants' progress following the initial brief intervention. Participants meeting study criteria will participate in the activities as outlined below. Table 5 details the schedule of assessment for responders (i.e., teens engaging in no more than normative substance use following the brief intervention) and non-responders (i.e., teen engaging in more than normative substance use following the brief intervention). Participants who are initially identified as responders, may be subsequently identified as non-responders should there be evidence of non-normative use at any of the assessment points from 6 to 18 months. Once identified as a non-responder, participants are randomized to one of the three previously described treatment conditions. The post-treatment assessment point will occur 6 months after the start date for the treatment. The 1-year follow-up will occur 1 year after the post-treatment assessment.

Parents and teens will each receive \$25 in gift cards upon completing each assessment point with the exception of the 9, 15, and 18-month screens. For the 9-month, 15-month, and 18-month screens, each teen who completes the assessment will receive \$25 in gift cards. Teachers will receive a \$10 gift card each time they return completed measures.

Table 5. Assessment measures Study 1

Baseline Diagnostic Measures	All Participants				Responder	Non-Responders				
	Intake	6-Month	9- Month Screen	12- Month	15- Month Screen	18- Month Screen	24- Month	Random- ization Visit ¹	Post-Tx	1-Year Follow-Up
Telephone Screening	Р							-		
Diagnostic Interview Schedule for Children (DISC-IV; Shaffer et al., 2000)										
ADHD Module	Р									
ODD Module	P		-							
CD Module	Р							-		
Parent Report of Son/Daughter Substance Abuse (PRASU) Baseline Version	Ρ									
Parent Report of Son/Daughter Substance Abuse (PRASU) Past 3 month Version		Ρ		Ρ			Ρ	Ρ	Р	Ρ
Family Information Form	Р									
Clinical Intake Interview	Р									
Adolescent Diagnostic Interview - Baseline Version (ADI ITAS Baseline) Adolescent Diagnostic	A							-		
Interview - Past 3 Month Version (ADI ITAS Past 3 Month)		A		A			A	A	A	A
Wechsler Abbreviated Scale of Intelligence - 2nd Ed (WASI-II; Wechsler, 2011)										
Vocabulary	A									
Matrix Reasoning	A		-							
Wechsler Individual Achievement Test - 3rd Ed. (WIAT-3; Wechsler, 2002)										
Word Reading	А									

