Spelling	A		_							
Numerical Operations DBD - RS (Pelham et al., 1991) - DSM-V Version	A									
DBD-RS Parent Report	Р	Р		Р			Р	Р	Р	Р
DBD-RS Adolescent Report	A	А		A			A	A	A	А
DBD-RS Teacher Report Impairment Rating Scale (Fabiano et al., 2006)	Т									
IRS Parent Report	Р	Р		Р			Р	Р	Р	Р
IRS Adolescent Report	A	A	L	A			A	A	A	A
IRS Teacher Report Short CBCL/YSR (Achenbach, 2009)	Т									
CBCL/YSR (Achenbach, 2009)	Р	Р	1	P			Р	Р	Р	Р
YSR	A	A		A			A	A	A	A
Treatment History Form	P	P		P			P	P	P	P
Primary Outcome Measures Substance Use Questionnaire Baseline Version (Molina &	A		F							
Pelham, 2003) Substance Use Questionnaire Past 3 Month Version (Molina & Pelham, 2003)		A	A	A	A	A	A		A	A
E-Cigarette Questionnaire ITAS Baseline Version	А									
E-Cigarette Questionnaire ITAS Past 3 Months Version		А	А	А	A	A	А		A	А
Current Substance Use (urine screen)	А	А	A	А	A	A	A		A	А
Secondary Outcome Measures & Potential										

Moderators										
Peer Substance Use and Peer Tolerance of Substance Use (Johnston et al., 1988)	А	A		A			A	A	A	А
Academic Functioning (GPA) - Grade Portal Log	School	School		School			School	School	School	School
Conflict Behavior Questionnaire (CBQ; Robin &										
Foster, 1989)	Р	Р	-	Р			Р	П	P	D
CBQ Parent CBQ Teen	Р А	A	-	P A			A	P A	P A	Р А
Parent Monitoring Scale (Steinberg et al., 2001)	A	A		A			A	A	A	A
Child Disclosure Scale (Stattin & Kerr, 2000)	А	А		A			А	А	А	А
Deviant Behavior Subscale - Teen Version Baseline (PEI; Winters)	A									
Deviant Behavior Subscale - Teen Version Past 3 Months (PEI; Winters)		A		A			А	A	А	А
Deviant Behavior Subscale - Parent Version Baseline (PEI; Winters)	Р									
Deviant Behavior Subscale - Parent Version Past 3 Months (PEI; Winters)		Р		Р			Р	Р	Р	Р
Brief Situational Confidence Questionnaire (Sobell, 1996)	А	A		A			A	A	А	А
Problem Recognition Questionnaire (Cady et al., 1996)	А	A		A			A	A	A	A
Expectancies Questionnaire	А	А		А			А	А	А	А
Likelihood of Future Use	А	A	A	A	A	Α	A	A	A	А
Mann Family Tree Brothers and Sisters (PALS)	Α		_							
Motives for Drinking (Cooper; PALS) - Baseline Motives for Drinking (Cooper;	А									
PALS) Marijuana Motives Measure		A		A			A	A	A	A
(Comeau) - Baseline Marijuana Motives Measure	Α									
(Comeau) Fagerstrom Test for Nicotine		A		A			A	A	A	A
Dependence (1-7 on PALS NDS)	PA	A		A			A	А	A	А
Mann Family Tree (PALS)	Р									
Marijuana Use Questionnaire	Р									
AUDIT	Р									
Abuse Columns (PALS)	Р									

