Alcohol Use Questionnaire	P									
Cigarette Use Questionnaire (PALS)	Р									
Bidimensional Acculturation Scale	PA									
Treatment History Form	Р	Р	Р	Р	Р	Р	Р	Р	Р	Р
Readiness to Change Ruler (Miller)	Α	A		A				Α	A	Α
IGIC-R (Trucco) Note P=Parent A=Adolescent T	A									

Note. P=Parent. A=Adolescent. T=Teacher.

¹ These measures will only be completed by families who are randomized following the 9, 15, or 18-month screening point.

Interventions. The Brief Intervention will be a brief early intervention program based upon Teen Intervene, an early intervention designed by Winters (Winters & Leitten, 2007). Due to the known executive functioning

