Aim 1: We will investigate response to a brief early intervention (BEI) for substance use among adolescents with ADHD. We hypothesize that approximately 50% of adolescents will show meaningful response to the BEI, as evidenced by no more than normative substance use assessed at 6-months following treatment. Aim 2: We will also test whether key variables associated with ADHD (ADHD symptoms) and with the development of substance use (parental monitoring, social impairment, academic functioning, family conflict, deviant peer affiliation and peer drug use, risky sexual behavior, delinguency, teen motivation and selfefficacy) predict response to the BEI. It is expected that poor response to treatment will be associated with high ADHD symptomatology, concurrent delinquency, risky sexual behavior, deviant peer affiliations, academic impairment, family conflict, lack of parent monitoring, poor self-efficacy and high motivation to use substances. Aim 3: We will also examine relative efficacy between the randomized second level interventions for BEI nonresponders (i.e., no treatment control, augmented psychosocial treatment (PT/ACBT) and combined medication and PT/ACBT) for non-responders to the BEI treatment. Adolescents who do not respond to the BEI and are randomized to the intervention arms of (PT/ACBT) or combined intervention (PT/ACBT+MED) will show differential improvements in primary and secondary outcomes (see Table 5). We hypothesize that relative to the no treatment control group, both groups will show improvements, with the largest effects for those who receive PT/ACBT+MED. Secondary analyses will be conducted for the one-year follow-up assessment for all groups. It is expected that therapeutic gains will extend through the follow-up period. Secondary analyses of treatment-related changes in the associated variables listed above will examine whether these changes mediate improvements in substance use. Analyses

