Aim 3: The third aim is to determine if, given nonresponse to the BEI, it is preferable to augment treatment with enhanced psychosocial intervention or multimodal treatment. As previously stated, we expect less than 50% of the sample to respond to the BEI, leaving at least 150 treatment-resistant adolescents to be randomized into one of the three treatment arms: (1) No treatment, (2) PT/ACBT, (3) PT/ACBT + MED. Using the general linear modeling techniques as implemented by SAS PROC GLM, we will examine differences between the treatment arms over post-treatment and one year follow-up measurement points with fixed effects of treatment arm. Analyzing each time period will address separate questions about the effect of intervention immediately post-treatment and at one-year follow-up. For these analyses, mixed linear models and/or GEE strategies will be used (Hedeker et al., 2006). Primary and secondary outcome measures will be evaluated separately (see Table 5). As our sample size permits, as a secondary analysis, we will also examine whether changes in the secondary outcomes listed above following treatment mediate response to treatment and substance use during the follow up phase.

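### The Aim 3 model names treatment arm as its only fixed effect and leaves out the pre-randomisation outcome, which the trial already schedules

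*Combined protocol and SAP*

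**What the plan says.** The Aim 3 paragraph under Analyses will "examine differences between the treatment arms over post-treatment and one year follow-up measurement points with fixed effects of treatment arm". It goes on to allow mixed linear models and/or GEE but lists no further terms. The Aim 3 hypothesis, in Hypotheses and Data Analysis, is worded as change: the two active arms will "show differential improvements in primary and secondary outcomes".

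Covariates are stated elsewhere, for other analyses. Age is named where the evaluation of the brief intervention (BEI) is described. Age, ethnicity, family SES, gender and ADHD-related impairment are named under Aim 1. Neither list is carried to Aim 3, and neither contains a pre-randomisation outcome.

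The pre-randomisation values exist:

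- **Primary outcomes.** Research Design and Methods randomises "Adolescents who do not demonstrate a response to the BEI at the 6, 9, 12, 15, or 18 month assessment". In Table 5 the row "Substance Use Questionnaire Past 3 Month Version" is marked at all five of those assessments, at post-treatment and at one-year follow-up. Its randomisation-visit cell is blank, so the SUQ that triggered randomisation is the last one before it.
- **Secondary outcomes.** Families "complete an assessment battery at the randomization point as outlined in Table 5 unless randomization occurs immediately following the 6 or 12 month assessment". Table 5, footnote 1 agrees: "These measures will only be completed by families who are randomized following the 9, 15, or 18-month screening point".

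**The concern.** Randomisation makes the arm-only comparison unbiased with valid type I error, so the stake is efficiency. Arms of about 50 are small, and a measure of the same behaviour, taken with the same instrument just before randomisation, is the obvious covariate. The arm-only model leaves the variance it explains in the error term.

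There is a second, practical risk. The hypothesis speaks of improvement, but the plan never says improvement from what. Intake, the 6-month assessment and the qualifying assessment are all candidates, and for a teen randomised at 18 months they lie far apart. An analyst could reasonably turn to raw change scores, which at low correlation do worse than using no baseline at all.

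**Working it through.** **Inputs from the Power Analysis section.** N = 150, 15% dropout, effect size .40 (metric not named), stated power .90. Alpha .05 two-sided is stated for Aim 1 and assumed here. r = .25 is stated for the medication-interaction analysis; none is given for Aim 3.

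**Assumptions.** 1:1:1 allocation, so 150 × .85 / 3 = 42.5 completers per arm; r = .10 and .50 as bounds; a normal approximation for use-day counts. "The 1-year follow-up will occur 1 year after the post-treatment assessment", and post-treatment is 6 months after treatment starts. The last outcome is therefore about 18 months after treatment start, and its r may be nearer the low bound.

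**The plan's .90.** No test is named, so several were tried at about 127 completers:

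| Reading of .40 | Power |
|---|---|
| Pairwise d = .40 | .445 |
| One-way three-arm test, f = .20 | .500 |
| One-way three-arm test, f = .40 | .985 |
| 3 arms × 2 times interaction, f = .20, r = .25 | .913 |
| One-way, arm means 0, .4, .8 SD | .913 |

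The last two share one noncentrality: .04 × 127 × 2 / .75 = 13.55, and .16 × (2/3) × 127 = 13.55. The basis of .90 therefore cannot be identified.

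**Effect of adjustment, pairwise.** The unadjusted noncentrality is .40 × √(42.5/2) = 1.844 on 83 df, giving power .445. Adjusting for a baseline with correlation r multiplies the SE by √(1 − r²). The equivalent randomised N is 150/(1 − r²).

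| r | SE multiplier | Power at d = .40 | Equivalent N | Power at d = .60 | Power at d = .80 |
|---|---|---|---|---|---|
| none | 1 | .445 | 150 | .780 | .954 |
| .10 | .995 | .449 | 152 | .784 | .956 |
| .25 | .968 | .469 | 160 | .806 | .964 |
| .50 | .866 | .557 | 200 | .884 | .988 |

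The d columns span the .40 to .80 range that the Power Analysis cites. Completers per arm needed for .90 power at d = .40 are 133 unadjusted, 125 at r = .25 and 100 at r = .50. If .40 is Cohen's f, power goes from .985 to about .99 at r = .25.

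**Raw change scores.** Their variance is 2(1 − r) times the outcome variance. At r = .25 that is 1.5, the effective d is .40/√1.5 = .327, and power is .319. They equal the unadjusted analysis only at r = .50.

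**Chance imbalance.** The baseline difference between two arms has SD √(2/42.5) = .217. Of this, r × .217 carries into the unadjusted estimate: .054 SD at r = .25 and .108 SD at r = .50. This is the same variance as the SE reduction, since √(.217² − .054²) = .210 = .217 × .968. It is not a second benefit.

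**Degrees of freedom, at r = .25.** Power is .4691 with no df charged for covariates, .4689 with 2, .4688 with 3 and .4683 with 7. One more, for baseline × visit, gives .4682.

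**The case against.** The strongest case is that this is a small efficiency suggestion. At the only correlation in the documents the gain is .024 in power (.469 − .445) and 3% in SE; at r = .10 it is .004. The one sizeable gain needs an assumed r of .50. Entry also requires non-normative use at the baseline assessment itself, which may restrict its range and lower r. All of this stands and limits the size of the point.

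It can also be said that a short sketch is being read as an exclusion. The text does not say arm alone, it allows mixed models and GEE, and the planned mediation analysis uses changes in secondary outcomes, which need pre-treatment values. If the interaction that gives .913 used a pre and a post measurement, a baseline was already in mind. That is possible but cannot be shown. The Aim 3 text names post-treatment and one-year follow-up as its time points and has no arm-by-time term, and no sentence puts a pre-randomisation outcome in the model. The .445 figure does rest on the pairwise reading.

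A simulation with skewed use-day counts gave SE ratios of 1.00, .97 and .87 at r = .10, .25 and .50. It set r, and fitted the model, on the log(1 + days) scale, so this agreement is partly built in. It adds little support.

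**Conclusion.** The concern holds. The only model statement for the randomised comparison names arm and no pre-randomisation outcome, although the primary instrument is scheduled at all five qualifying assessments. On the pairwise reading with 42.5 completers per arm, adjustment moves power at d = .40 from .445 to .469 at r = .25, with .449 and .557 at the assumed bounds. It is negligible if .40 is Cohen's f, and no r in the range used reaches .90 on the pairwise reading. Validity is not at stake. The change should be made because it improves the only randomised comparison with data already scheduled, and because naming the baseline closes off change scores and any choice of baseline after the results are seen.

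**What to change.** State in the Aim 3 analysis:

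1. **Model.** Arm, visit and arm × visit, fitted either as ANCOVA with a baseline × visit term or as a baseline-constrained mixed or GEE model. Adjust for the same outcome before randomisation and for age.
2. **Primary baseline.** The SUQ value from the qualifying 6-, 9-, 12-, 15- or 18-month assessment, not intake.
3. **Drinks per drinking day, if carried into Aim 3.** Because "non-normative use of any psychoactive substance will be considered non-response", a teen can be randomised for marijuana or other drug use alone. With no drinking days at the qualifying SUQ, set the baseline to 0 and add an any-drinking indicator.
4. **Secondary baselines.** The randomisation-visit battery after a 9-, 15- or 18-month trigger; the 6- or 12-month assessment when randomisation follows it directly.
5. **Change scores.** Do not use raw change as the outcome. Adjustment for the visit of randomisation is optional.

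The cost is SAP wording and a baseline rule for each outcome, with no new data collection. Baseline and age take 2 df, the drinking indicator makes 3, four visit indicators make 7 and baseline × visit makes 8; the power lost is .001 or less.

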The Parent Training and Adolescent CBT (PT/ACBT) will be longer in duration than the BEI (12-family sessions with individual adolescent, parent, and joint adolescent and parent time), and will include additional parent training in behavioral modification, adolescent and parent contracting, and adolescent decision making skills. The PT/ACBT and Medication (PT/ACBT+MED) condition will be identical to the PT/ACBT condition but will include concurrent stimulant medication administration. Recruitment will continue on a rolling basis over the course of the year. The primary outcome measure will be alcohol and marijuana use. Secondary outcome measures include adolescent ADHD symptom severity, situational impairment (e.g., academic and social impairments, parental monitoring), proximal deviancy measures (e.g., delinquency, deviant peer affiliations, risky sexual behavior, family conflict), and teen attitudes and beliefs (motivation to use, self-efficacy). (see Table 5).

Participants. Three-hundred adolescents with ADHD between the ages of 12-16 who displayed elevated risk for substance use problems (but not severe abuse of alcohol, marijuana, or other drugs) will be recruited beginning in YR01 of the project on a rolling basis. Elevated risk is defined as the presence of at least risk factor from each of the following two categories of risk:

- 1. General Risk Factors
 - a. Elevated symptoms of ODD or CD (Elevated parent or teacher scores on relevant subscales of the CBCL, TRF, or the DBD-RS).
 - b. Elevated conflict with parents (Elevated parent-reported conflict on the CBQ)
 - c. Low parental monitoring (Parents are aware of teen activities or teens disclose activities to parents only some of the time or less often.)
 - d. Academic failure (Teens have previously failed a grade in school or earned Ds or Fs on most recent report card.)
- 2. Substance Use Specific Risk Factors
 - a. Adolescent non-normative use of alcohol or other drugs indicated either by a positive urine drug screen or by adolescent self-report on the Substance Use Questionnaire.
 - Adolescent use of cigarettes or e-cigarettes indicated by self-report on the SUQ or the E-Cigarette Questionnaire.
 - c. Elevated parental use of alcohol or other drugs indicated by AUDIT score of 8 or higher or parent self-report of any use of other drugs for non-medical reasons.

Revised Protocol Version 06042019

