deficits associated with ADHD, this program will be modified to be longer in duration (5 sessions). Primarily the teen will meet individually with the clinician for the sessions; however, the parent will join the teen for portions of some sessions. These sessions will have additional focus on decision making skills, as these are believed to have a direct impact on the characteristic impulsivity of ADHD. The standard Teen Intervene (Winters & Leitten, 2007) is a brief, outpatient intervention geared at reducing alcohol and drug use in adolescents and youth at risk for developing substance use problems. The standard program consists of three 60-minute, oneon-one therapy sessions that employ motivation and self-change techniques. The first session elicits information about the individual's substance use and its related consequences, evaluates the student's willingness to change, and helps the individual set goals that he or she would like to pursue. The second session reviews the patient's progress toward reaching goals, discusses high-risk situations that have caused difficulty in reaching the goals, discusses strategies to overcome these barriers, and negotiates the continuation of goals. A third session is conducted with the adolescent's parent. This session also uses motivational goal setting and addresses the following topics: a) The adolescent's substance use problem, b) the parent's attitudes or behaviors towards the substance use problem, c) parental monitoring and supervision, and d) healthy substance use behaviors and attitudes by the parent. The proposed modification of the Teen Intervene builds on this content with additional emphasis on problem-solving skills, management of emotion triggers of substance use, and skills for resisting peer pressure to use substances. Evaluation of treatment response will include the following outcome measures based upon the Substance Use Questionnaire for the past 90 days: Number of alcohol use and marijuana use days will be examined as a combined variable and will be examined separately. For alcohol, separate analyses will also be conducted for number of drinks per drinking day. Age will be employed as a covariate in these analyses to account for developmental differences between early and late adolescence.

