Power Analysis: For Aim 1, previous evaluations of BEI report a large effect of treatment on days of alcohol use (d=2.67; Winters et al., 2007). A sample size of 300 (G*Power 3.1.2 software), with alpha of 0.05 for a two-tailed test, will provide power = 0.96 to detect a small treatment effect size of 0.25 if there are no drop outs. Assuming a maximum dropout rate of 15%, as shown in previous studies with Hispanic adolescents with behavior problems (Pantin et al., 2009; Prado et al., 2007), the power drops slightly to 0.90. We also plan to measure the impact of concurrent medication use on treatment effect. For this analysis there are now two groups of participants, those currently using stimulant medication and those not using stimulant medication. The sample size of 300 with a maximum drop-out rate of 15% will provide .90 power to detect an interaction effect of medication, assuming a small pre-test to post-test correlation among measures (r = .25). For Aim 3, a sample size of 150 with a maximum drop-out rate of 15% will provide .90 power for a treatment effect size of .40, which is adequate considering that most ES for similar treatments range between .40 and .80 (Waldron & Turner, 2008). Thus, the sample should be sufficient to detect significant effects of treatment as well possible prediction models.

c. Potential Risks

Risk: Participants may experience mild and transitory psychological discomfort from completing research measures that deal with emotionally laden material, including reporting on illicit drug use and other antisocial or illegal behaviors, which may be uncomfortable for some participants. **Procedure:** We will inform participants of the NIH Confidentiality Certificate prior to collecting any data for the study, which will shield the research data from a subpoena or court order. In addition, participants and their parents will be advised to ask questions of study personnel if confidentiality is of a concern, and to refrain from answering questions that cause them personal distress.

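### Aim 3 names no single primary variable and no testing order, so its post-treatment comparisons carry a false-positive risk well above .05

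*Combined protocol and SAP*

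**What the plan says.** All references are to the combined protocol and SAP.

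- **Primary outcome.** Research Design and Methods: "The primary outcome measure will be alcohol and marijuana use". This is a domain, not a variable.
- **Variables.** The Brief Intervention paragraph under Interventions, on evaluating treatment response: "Number of alcohol use and marijuana use days will be examined as a combined variable and will be examined separately". It adds a separate analysis of drinks per drinking day. That makes four variables from the Substance Use Questionnaire (SUQ), none ranked above the others.
- **Instruments.** Under its primary heading, Table 5 lists the SUQ, the E-Cigarette Questionnaire and the urine screen.
- **Hypothesis.** Under Hypotheses and Data Analysis, Aim 3 predicts that both active arms beat the no-treatment control and that the arm with medication does best. The same paragraph calls the one-year analyses secondary.
- **Analysis.** Under Analyses, the Aim 3 paragraph fits treatment arm as a fixed effect, analyses post-treatment and one year as separate questions, and points to Table 5: "Primary and secondary outcome measures will be evaluated separately".
- **Error rate.** The only stated level is in the Aim 1 power sentence: "with alpha of 0.05 for a two-tailed test". Aim 3 gives none. The one other mention of type I error concerns missing data. No multiplicity rule or testing order appears.

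**The concern.** An omnibus arm test alone cannot show that each active arm beats control, or that adding medication beats psychosocial treatment alone. The Aim 3 hypothesis therefore needs pairwise contrasts. With four candidate outcomes and no rule for choosing among them, any one significant contrast could be offered as support, and the choice could be made after the results are seen.

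The stakes are highest in Aim 3 because the brief intervention stage has no control group. The Aim 3 result would bear on whether adolescents who do not respond are offered twelve further family sessions, with or without stimulant medication.

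**Working it through.** **1. The plan's own figure.** The Power Analysis assumes "a sample size of 150 with a maximum drop-out rate of 15" per cent and states that this "will provide .90 power for a treatment effect size of .40". It does not say which test or effect-size metric is meant.

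- Analysed N: 150 × .85 = 127.5, taken as 127.
- The figure comes back for one three-arm, two-occasion group-by-time test on one outcome, with f = .40/2 = .20 and r = .25. The plan states that r for the medication interaction; its use here is an assumption.
- Noncentrality = f² × N × m/(1 − r) = .04 × 127 × 2/.75 = 13.55. With 2 and 124 degrees of freedom at .05, power = .913, against the stated .90.
- Other readings miss. A one-way test with f = .40 gives .985, and a single-occasion pairwise test with d = .40 gives .45.

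The stated power therefore corresponds to one outcome and one test at the full .05. It leaves no allowance for several outcomes.

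**2. Size of the family.** Four SUQ variables × three contrasts = 12 tests at post-treatment. Counting the other Table 5 primary instruments would raise this.

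**3. Bound if the tests were independent.**
- Any direction: 1 − .95^12 = .460.
- Benefit direction, .025 per test: 1 − .975^12 = .262.

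**4. Allowing for dependence.** The tests share arms, and the combined score is the sum of two of the others. Simulation under no true effects used 42 per arm (127/3, equal allocation assumed), normal outcomes, combined days = alcohol + marijuana, and assumed outcome correlations from 0 to .8.

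| Post-treatment family | At least one false positive, any direction | Benefit direction |
|---|---|---|
| One outcome, omnibus test first | .05 | – |
| One outcome, three contrasts, no gate | .12 | .064 |
| Four outcomes, contrasts gated by each outcome's own omnibus test | .10–.17 | .06–.10 |
| Four outcomes, 12 tests, no gate | .22–.35 | .12–.21 |

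The lower ends belong to the strongest correlations. Without a gate, the any-direction rate is .22/.05 = 4.4 to .35/.05 = 7 times the nominal level. With a gate per outcome it is 2 to 3.4 times.

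**5. Power under the alternatives.**
- One outcome with the omnibus test at .05 keeps the .913 of step 1.
- Splitting alpha over four outcomes (.05/4 = .0125) lowers the omnibus power to .79.
- Splitting over 12 pairwise tests (.05/12 = .00417) lowers pairwise power at d = .40 from .845 to .528 (85 in two arms, r = .25).
- On a single post-treatment occasion, with 42 per arm and both active arms at d = .40, power for each active-versus-control contrast is about .44 without a gate and about .36 behind the omnibus gate.

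**The case against.** A reader might infer that the plan sets up 24 primary-level tests (four outcomes, three contrasts, two times) and that a false claim of benefit is likely. The documents do not support either.

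- **Twenty-four tests.** The hypothesis section already makes the one-year analyses secondary, which halves the family. The any-direction rate of .41 to .58 over both times therefore does not describe the primary-level risk.
- **Likely false benefit.** The any-direction rates include results in which a treatment looks worse. In the benefit direction the simulated rates are .12 to .21 at post-treatment and .21 to .37 over both times. Even 24 independent tests give 1 − .975^24 = .455. None reaches one half.

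Further points on the plan's side are fair:

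- **Level and contrasts.** Aim 3 states neither a .05 level nor pairwise tests, and a fixed arm effect naturally yields an omnibus test. If that test is an unwritten gate, the error falls to .10 to .17. This is the most favourable multi-outcome reading, and it is still at least double .05.
- **The four variables.** They are listed for response to the brief intervention, so their use in Aim 3 is an assumption. But Aim 3 offers no other definition and points to a table with several primary instruments.
- **The word separately.** It may mean only that primary and secondary tiers are kept apart. That would still not choose among the variables within the primary tier.

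**Conclusion.** The concern holds for the post-treatment comparison. With no designated primary variable and no testing order, the chance of at least one false positive under no true effects is about .22 to .35 if 12 tests are run at .05 (about .12 to .21 for false benefit). It is about .10 to .17 if each outcome has its own omnibus gate. One named outcome with a gate gives .05.

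The figures rest on equal allocation, normal outcomes, the assumed correlations, the carry-over of the four SUQ variables to Aim 3, and the .05 level borrowed from Aim 1. The exact size moves with these assumptions. The direction does not: on every multi-outcome reading examined, the error is well above .05.

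**What to change.** Before outcomes are examined by arm, amend the Aim 3 analysis paragraph to do four things:

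1. Name one SUQ variable at the post-treatment assessment as the Aim 3 primary. Combined alcohol-and-marijuana days over the past 90 days is a natural choice because it covers both substances in the stated primary outcome. The documents do not rank the four, so the choice is the sponsor's.
2. Test the three arms together at two-sided .05, and test the pairwise contrasts at .05 only if that test is significant. With exactly three arms this controls the family-wise error without splitting alpha: if no arms differ, the omnibus test holds .05, and if only two arms are equal, only one true null contrast remains.
3. Label the other SUQ variables, and the other instruments under Table 5's primary heading, secondary for Aim 3.
4. Repeat in this paragraph that the one-year results are secondary, as the hypothesis section already says.

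The cost is one paragraph of text. Separate alcohol, marijuana and quantity results could no longer carry the main claim. The gate also lowers power for each active-versus-control contrast, from about .44 to .36 in the single-occasion case above. The omnibus power that matches the plan's stated .90 is unchanged.
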